- Tumor types and corresponding treatment combinations to be evaluated will be identified prior to Phase IIA commencement with patients enrolled separately into tumor-specific arms of 20 patients each. This change will be documented in a protocol amendment before it occurs.
- The need for futility criteria to be evaluated in any of the arms following enrollment of a pre-defined number of patients < 20 shall be determined at a later date depending on tumor types evaluated. This change will be documented in a protocol amendment before it occurs.
- For all potential patients, there will be up to a 30-day screening and eligibility assessment period prior to enrollment.

All patients will continue to receive their assigned treatment throughout the study until the occurrence of disease progression, death, or other unacceptable treatment-related toxicity, or until the study is closed by the sponsor.

C1: Cycle 1; DLT: dose limiting toxicity; IO: immuno-oncology; RP2D: Recommended Phase II dose *MTD = one dose lower than discontinued dose

3.1.3 **Dose-limiting Toxicities**

A DLT will be defined as the occurrence of any of the following hematologic or non-hematologic AEs that are considered definitely, probably, or possibly related to IMSA101 in the first 28 days (first cycle) of treatment. The severity of AEs will be graded according to CTCAE v5.0. For safety run-ins for Phase IIA combination arms, DLTs will be defined as DLT-qualifying events considered at least possibly related to the drug combination, including AEs already characterized for the partner drug.

Hematologic AEs

- \geq Grade 4 neutropenia lasting for > 7 days
- Febrile neutropenia (defined as absolute neutrophil count (ANC) < 1000/mm³ with a single temperature of 38.3°C (101°F) or a sustained temperature of 38°C (100.4°F) for > 1 h)
- ≥ Grade 4 thrombocytopenia, or Grade 3 thrombocytopenia associated with Grade ≥ 2 bleeding
- \geq Grade 4 anemia

Non-hematologic AEs:

- Elevation of alanine transaminase (ALT) or aspartate transaminase (AST) by \ge 3X upper limit of normal (ULN) with concurrent elevation of serum total bilirubin \ge 2X ULN
- Any ≥ Grade 3 non-hematologic AE of any duration will be considered a DLT with the following exceptions:
 - Nausea/vomiting/diarrhea:
 - To be considered a DLT, ≥ Grade 3 nausea/vomiting/diarrhea must be refractory to supportive care and last > 3 days.
 - \geq Grade 3 nausea/vomiting/diarrhea that lasts \leq 3 days is not a DLT.
 - Fatigue:
 - To be considered a DLT, \geq Grade 3 fatigue must last > 7 days.
 - \geq Grade 3 fatigue that lasts \leq 7 days is not a DLT.

3.1.4 Maximum Tolerated Dose/Recommended Phase II Dose

The MTD is defined as the highest dose level of IMSA101 at which no more than 1 out of 6 (7 when applicable) patients experiences a DLT during the first cycle (28 days) of therapy.

The MTD/RP2D of IMSA101 will be determined by the sponsor and the CRC.

The RP2D is defined as the dose (either at MTD or below MTD) that is selected for evaluation in the Phase IIA component of the study.

3.2 STOPPING RULES

The entire study or treatment of individual patients may be stopped under defined circumstances as outlined in Section 7.

3.3 COHORT REVIEW COMMITTEE

An independent CRC will be organized to review the safety of IMSA101 during the study. The CRC will be composed of principal investigators (and their representatives), medical monitor, and sponsor representatives. Prior to escalating to next dose level, this committee will review all available safety data and determine whether to proceed with escalation. Meeting results will be documented and formal notification of decisions will be provided to all participants.

3.4 BLINDING AND RANDOMIZATION

This is an open-label and non-randomized study; no blinding and randomization will be conducted.

4 SELECTION OF PATIENTS

4.1 NUMBER OF PATIENTS

Approximately 115 patients are expected to be treated in this study.

- Phase I: approximately 45 patients in 5 dose cohorts. Any patient who discontinues the study before completing Cycle 1 (and before receiving all 3 doses of IMSA101) for reasons other than DLT, will be replaced.
- Phase IIA: approximately 70 patients in 3 arms of approximately 20–25 patients each. Any safety lead-in patient who discontinues the study before completing Cycle 1 (and before receiving all 3 doses of IMSA101) for reasons other than DLT, will be replaced.

4.2 INCLUSION CRITERIA

Patients meeting all of the following criteria will be considered for enrollment into the study.

Phase I combination only:

- 1. Eligible patients will meet one of the following criteria:
 - Have radiographically-confirmed RECIST stable disease through ≥ 2 consecutive cycles of an approved PD-1 or PD-L1 targeted ICI administered as monotherapy
 - Be clinically stable following a first (unconfirmed) follow-up radiographic scan demonstrating progression of disease on ICI monotherapy
 - Have progression through prior ICI therapy administered either as mono or combination therapy
 - Have received no prior ICI therapy but otherwise be ineligible for all available standards of care
- 2. Have experienced no prior Grade \geq 3 CTCAE adverse events on ICI therapy that were considered by the investigator to be at least possibly ICI drug-related.

All patients (unless otherwise indicated):

- 1. Signed informed consent and mental capability to understand the informed consent
- 2. Male or female patients \geq 18 years of age
- 3. Histologically or cytologically documented locally advanced or metastatic solid tumor malignancies refractory to or otherwise ineligible for treatment with standard-of-care agents/regimens, including but not limited to:
 - Malignant melanoma
 - Hormone receptor negative breast cancer
 - Gastro-esophageal cancer
 - Non-small cell lung cancer

- Head and neck cancer
- Hepatoma
- Renal cell carcinoma
- 4. Eastern Cooperative Oncology Group (ECOG) performance status of ≤ 1 (Appendix 13.1)
- 5. Evaluable or measurable disease as follows:
 - 2 or 3 RECIST evaluable lesions: one that is suitable for injection and biopsied; an optional non-injected second lesion that will be biopsied for abscopal effect (only 1 patient per cohort required to have non-injected lesion biopsied; optional for all other patients in that cohort); and one measurable lesion that will be followed for response only.
 - Injectable tumors shall be accessed by intralesional (cutaneous) or percutaneous injection only, including those lesions that are visible, palpable, or detectable by standard radiographic or ultrasound methods. Neither surgical procedures nor endoscopically-guided injections including those to endobronchial, endoluminal, or endosinusoidal spaces shall be allowed. While no anatomic locations are required or disallowed, lesions selected for intratumoral injection must, in the opinion of the investigator:
 - Not be immediately adjacent to blood vasculature or other physiologic landmarks in such a way that will accrue undue safety risk to the patient
 - Have longest diameter $\geq 10 \text{ mm}$ and $\leq 50 \text{ mm}$
 - Be fully evaluable per RECIST v1.1 criteria (Appendix 13.2)
- 6. Life expectancy > 3 months (Phase I) and > 6 months (Phase IIA)
- 7. ECG without evidence of clinically meaningful conduction abnormalities or active ischemia as determined by the investigator
- 8. Acceptable organ and marrow function as defined below:
 - Absolute neutrophil count > 1,500 cells/ μ L
 - Platelets > 50,000 cells/ μ L
 - Total bilirubin ≤ 1.5 times the ULN
 - AST/ ALT \leq 2.5 X ULN. If liver metastases are present, AST/ALT < 5 times ULN
 - Serum creatinine < 1.5 mg/dL and a measured creatinine clearance ≥ 50 mL/min using the Cockcroft-Gault formula (Appendix 13.3)
 - Prothrombin time (PT)/partial thromboplastin time (PTT) \leq 1.5 times ULN
- 9. Women of child-bearing potential (defined as a female who has experienced menarche and who has not undergone successful surgical sterilization (hysterectomy, bilateral salpingectomy, or bilateral oophorectomy) or is not postmenopausal (defined as amenorrhea for at least 12 consecutive months with an appropriate clinical profile at the appropriate age, e.g., greater than 45 years) must have a negative serum pregnancy test prior to first dose of study drug
- 10. Male and female patients with reproductive potential must agree to use two forms of highly effective contraception throughout the study

4.3 EXCLUSION CRITERIA

All patients:

- 1. Anti-cancer therapy within 4 weeks or \leq 5 half-lives of the first dose of study drug
- 2. Failure to recover, to Grade 1 or less, from clinically significant AEs due to prior anti-cancer therapy, as judged by the investigator.
- 3. Known untreated brain metastases or treated brain metastases that have not been stable (scan showing no worsening of CNS lesion[s] and no requirement of corticosteroids) ≥ 4 weeks prior to study enrollment
- 4. Baseline prolongation of QT/QTc interval (QTc interval > 470)
- 5. Uncontrolled intercurrent illness (including, but not limited to, ongoing or active infection, symptomatic congestive heart failure, unstable angina pectoris, cardiac arrhythmia, or psychiatric illness/social situations) that in opinion of the investigator would limit compliance with study requirements
- 6. Women who are pregnant or breastfeeding
- 7. Sponsor reserves right to exclude any patient from the study on basis of pre-study medical histories, physical examination findings, clinical laboratory results, prior medications, or other entrance criteria.

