 - 2,400 µg (with an initial "priming" dose of 1,200 µg)
 - 3,600 µg (with an initial "priming" dose of 2,400 µg)
 - 4,800 μg (with an initial "priming dose" of 3,600 μg)
- Combination dosing of IMSA101 shall be evaluated in Phase I upon satisfaction of the following criteria:
 - A. A given dose level (combo dose level 1) has been confirmed as safe for monotherapy dosing (i.e., < 2/6 [7 when applicable] patients experience Cycle 1 DLT).
 - B. The next higher dose level (combo dose level 2) has been confirmed as safe for monotherapy dosing (i.e., < 2/6 [7 when applicable] patients experience Cycle 1 DLT).
 - C. The dose level (combo dose level 1) is found to demonstrate adequate IMSA101 PD activity based on exploratory endpoints.
- Eligible patients for Phase I combination dosing shall meet one of the following criteria:
 - have radiographically-confirmed RECIST stable disease through ≥ 2 consecutive cycles of an approved PD-1/PD-L1-targeted immune checkpoint inhibitor (ICI) administered as monotherapy
 - be clinically stable following a first (unconfirmed) follow-up radiographic scan demonstrating progression of disease on ICI monotherapy
 - have progression through prior ICI therapy administered either as mono or combination therapy
 - have received no prior ICI therapy but otherwise be ineligible for all available standards of care
- Phase I combo patients have experienced no prior Grade ≥ 3 CTCAE adverse events on ICI therapy that were considered by the investigator to be at least possibly ICI drug-related
- Phase I combo patients shall either receive de novo the combination of IMSA101 + an ICI of their investigator's choosing or, in cases where they are already receiving ICI monotherapy, have IMSA101 added to their current therapy such that Day 1 of IMSA101 shall represent Cycle 1, Day 1.
- A radiographic tumor assessment shall have occurred within 30 prior days of adding IMSA101 to current therapy.
- Phase I combination therapy IMSA101 doses of 800 µg and 1,200 µg will be administered by intratumoral injections each week for 3 weeks in Cycle 1 (Days 1, 8, and 15), and for

Sponsor:	Investigational Product:	Developmental Phase:	
ImmuneSensor Therapeutics	IMSA101	Phase I/IIA	

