 Women of child-bearing pe who has not undergone suc salpingectomy, or bilateral amenorrhea for at least 12 	ccessful surgical sterilization (hy oophorectomy) or is not postme consecutive months with an app er than 45 years) must have a ne	o has experienced menarche and ysterectomy, bilateral enopausal (defined as propriate clinical profile at the	
10. Male and female patients v highly effective contracept	vith reproductive potential must ion throughout the study	agree to use two forms of	

Sponsor: ImmuneSensor Therapeutics	Investigational Product: IMSA101	Developmental Phase: Phase I/IIA
Exclusion Criteria:		
All patients:		
1. Anti-cancer therapy within	4 weeks or < 5 half-lives of the f	irst dose of study drug
2. Failure to recover, to Grade cancer therapy, as judged b	e 1 or less, from clinically signific by the investigator.	cant AEs due to prior anti-
 Known untreated brain metastases or treated brain metastases that have not been stable (scan showing no worsening of CNS lesion[s] and no requirement of corticosteroids) ≥ 4 weeks prior to study enrollment 		
4. Baseline prolongation of Q	T/QTc interval (QTc interval > 4	70)
 Uncontrolled intercurrent illness (including, but not limited to, ongoing or active infection, symptomatic congestive heart failure, unstable angina pectoris, cardiac arrhythmia, or psychiatric illness/social situations) that in opinion of the investigator would limit compliance with study requirements 		
6. Women who are pregnant of	or breastfeeding	
7. Sponsor reserves right to exclude any patient from the study on basis of pre-study medical histories, physical examination findings, clinical laboratory results, prior medications, or other entrance criteria.		
Test Product, Dose and Mod	e of Administration:	
	levels of (but not necessarily be li atumoral injection as monotherap	
Combination therapy: IMSA101 in combination with current ICI therapy administered according to the label of that product. IMSA101 combination dose levels through intratumoral injection are as follows:		
• 800 and 1,200 µg		
 2,400 μg (with an initial "priming" dose of 1,200 μg) 		
 3,600 μg (with an initial "priming" dose of 2,400 μg) 		
 4,800 μg (with an initial "priming" dose of 3,600 μg) 		
1 mL IMSA101 total volume will be given as follows:		
Monotherapy: IMSA101 every week for 3 weeks in Cycle 1 (Days 1, 8, and 15) followed by every other week in Cycles 2+ (Days 1 and 15).		
Combination therapy:		

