 - have radiographically-confirmed RECIST stable disease through ≥ 2 consecutive cycles of an approved PD-1/PD-L1-targeted immune checkpoint inhibitor (ICI) administered as monotherapy
 - be clinically stable following a first (unconfirmed) follow-up radiographic scan demonstrating progression of disease on ICI monotherapy
 - have progression through prior ICI therapy administered either as mono or combination therapy
 - have received no prior ICI therapy but otherwise be ineligible for all available standards of care
- Phase I combo patients have experienced no prior Grade ≥ 3 CTCAE adverse events on ICI therapy that were considered by the investigator to be at least possibly ICI drug-related
- Phase I combo patients shall either receive de novo the combination of IMSA101 + an ICI of their investigator's choosing or, in cases where they are already receiving ICI monotherapy,

have IMSA101 added to their current therapy such that Day 1 of IMSA101 shall represent Cycle 1, Day 1.

- A radiographic tumor assessment shall have occurred within 30 prior days of adding IMSA101 to current therapy.
- Phase I combination therapy IMSA101 doses of 800 µg and 1,200 µg will be administered by intratumoral injections each week for 3 weeks in Cycle 1 (Days 1, 8, and 15), and for Cycle 2 and all other cycles thereafter, every other week on Days 1 and 15. Additional combination therapy IMSA101 doses of 2,400 µg, 3,600 µg, and 4,800 µg require the following priming dose on Day 1 of Cycle 1: 1,200 µg for the 2,400 µg dose group, 2,400 µg for the 3,600 µg dose group, and 3,600 µg for the 4,800 µg group. After Day 1 of Cycle 1, the full dose for these groups will be administered on Day 1 of Weeks 2 and 3 of Cycle 1 (i.e., weekly dosing 3 out of 4 weeks), and on Day 1 of Weeks 1 and 3 for all cycles thereafter (i.e., bi-weekly dosing).
- Safety evaluations and dose escalation of IMSA101 administered in combination with current ICI therapy shall proceed in a manner consistent with monotherapy escalation, with the exception of allowed de-escalation, and shall proceed independently of monotherapy dose escalation and evaluations.
- De-escalation: If ≥ 2 DLTs occur among the initial 3 (4 when applicable) or 6 (7 when applicable) patients, de-escalation of IMSA101 is allowed for the combination therapy dose levels as follows:
 - 2,400 μg may be de-escalated to 1,800 μg (with a priming dose of 1,200 μg on Day 1 of Cycle 1)

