8 TREATMENT

8.1 DOSING AND ADMINISTRATION OF IMSA101

IMSA101 is a sterile, nonpyrogenic solution containing 10 mg of IMSA101 in 1.0 mL of Prior to dosing, IMSA101 will be thawed and further diluted in order to be delivered intratumorally at the following dose levels:

Monotherapy: 100, 200, 400, 800, and 1,200 µg.

Combination Therapy IMSA101 + current ICI therapy (administered according to the label of that product):

- 800 and 1,200 µg
- 2,400 µg (with an initial "priming" dose of 1,200 µg)
- 3,600 µg (with an initial "priming" dose of 2,400 µg)
- 4,800 µg (with an initial "priming" dose of 3,600 µg)

This drug is **NOT SAFE** to be administered without proper dilution. Composition of IMSA101 is presented in Table 4.

Table 4Composition of IMSA101 for Injection

Ingredients	Grade	Function	Composition (1.2 mL per vial)

NF: National Formulary; USP: United States Pharmacopeia

8.1.1 **Preparation of IMSA101**

Prior to dosing, IMSA101 will be thawed and diluted **sectors** as detailed in a separate pharmacy manual. A single pre-defined tumor/tumor site per patient will be selected and injected intratumorally throughout study participation. Injections of tumors that are not superficial will be performed under image guidance.

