11.7 PROTOCOL AMENDMENT

Before the start of the study, the study protocol, informed consent document, and any other appropriate documents (or amendments) will be submitted to the appropriate authorities such as the FDA and/or local IRB/IEC with a cover letter or a form listing the documents submitted, their intended dates of issue, and the site (or region or area of jurisdiction, as applicable) for which approval is sought. If applicable, the documents will also be submitted to the authorities in accordance with local legal requirements.

The investigator should not implement any deviation from, or changes of, the protocol without agreement by the sponsor and prior review and documented approval from the IRB/IEC of an amendment. The only exceptions are where necessary to eliminate an immediate hazard(s) to study patients, or when the change(s) involves only logistical or administrative aspects of the study (e.g., change in monitor[s], change of telephone number[s]). Non-substantial protocol amendments may or may not be required to be submitted for approval/notification to the appropriate authorities (i.e., FDA, IRB/IEC).

As soon as possible, the implemented deviation or change, the reasons for it, and, if appropriate, the proposed protocol amendment(s) should be submitted:

- to the appropriate authorities for review and approval/favorable opinion
- to the sponsor for agreement

The party initiating an amendment must confirm it clearly in writing and it must be signed and dated by the sponsor and the principal investigator. The sponsor or its designee will ensure that the investigators submit necessary protocol amendments to the appropriate IRB/IEC.

All agreed protocol amendments must be clearly documented using standard procedures as defined by the sponsor, and must be signed and dated by the sponsor and the investigator.

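### Exclusion 1 bars Phase I combination patients who are still on a checkpoint inhibitor, the group to which section 3.1.1 says IMSA101 should be added

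*Combined protocol and SAP*

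**What the plan says.** Section 4.3 lists its exclusions for all patients. The first is "Anti-cancer therapy within 4 weeks or" at most five half-lives before the first dose of study drug. The synopsis repeats the rule under the same heading, with a slightly different inequality: "4 weeks or < 5 half-lives of the" first dose. Neither version has an exception.

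The combination part of section 3.1.1, and the matching part of the synopsis, give Phase I combination patients two ways to start. They may begin the ICI and IMSA101 together or, "in cases where they are already receiving ICI monotherapy, have IMSA101 added to their current therapy". For the second group Cycle 1 Day 1 is dated from the first IMSA101 dose.

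Section 4.2 offers four entry routes to the combination cohorts. Two describe patients who would normally still be on treatment: RECIST stable disease over at least two consecutive ICI cycles, and "Be clinically stable following a first (unconfirmed) follow-up radiographic scan demonstrating progression of disease on ICI monotherapy". Section 8.1 describes the regimen as "IMSA101 + current ICI therapy (administered according to the label of" the product, and the synopsis has similar wording.

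**The concern.** The intention to add IMSA101 to ongoing ICI treatment is plain. The difficulty is that eligibility is checked criterion by criterion at screening, and the criterion forbids what the design section directs. Section 11.7 says the investigator "should not implement any deviation from, or changes of, the protocol without agreement by the sponsor" and prior IRB/IEC approval of an amendment. Its exceptions cover immediate hazards and purely logistical or administrative changes, and neither fits.

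A site that applies exclusion 1 literally has three options:

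- refuse a patient whom the design invites;
- stop the ICI for a washout, which interrupts treatment in a patient who may have stable disease and is no longer an addition to current therapy;
- enrol the patient and record an eligibility violation.

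Sites may choose differently. The combination cohorts could then mix uninterrupted and washed-out ICI patients for a reason the design did not intend. Those cohorts set the combination RP2D, which is part of the primary objective.

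**Working it through.** The plan gives no figure to reproduce on this point. The check is a comparison of texts, followed by a bound on size.

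**1. Do the rules collide?** Exclusion 1 covers anti-cancer therapy, all patients, and a window ending at the first dose of study drug. The add-on instruction covers patients receiving an ICI when IMSA101 starts. An ICI is anti-cancer therapy, so a patient in the add-on group falls under exclusion 1 whenever the last ICI dose lies inside the window.

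**2. Is there an exception elsewhere?** The general inclusion list in 4.2 is headed so as to allow exceptions; the exclusion list in 4.3 is not. The concomitant-medication text (6.4, 8.3) and the dosing text (8.1) contain none. Reading study drug to include the ICI does not help, because 3.1.1 dates Cycle 1 Day 1 from IMSA101 and treats the ICI as already running.

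**3. How often does the window catch a continuing patient?** The documents give no ICI dosing interval or half-life. Assume an interval D of 14 to 42 days. A continuing patient's last ICI dose is then at most D days before Cycle 1 Day 1.

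- 4-week limb, D = 14, 21 or 28: the last dose is always within 28 days, so every continuing patient is barred.
- 4-week limb, D = 42: 28 of 42 possible start days are barred, 28/42 = 67%. As a share of patients, this also assumes that start days are spread evenly over the interval.
- Half-life limb, D = 42: the remaining 42 - 28 = 14 days are barred if 5 x t½ ≥ 42, that is t½ ≥ 42/5 = 8.4 days.
- If the two limbs are read as whichever is shorter, the 4-week limb still governs when 5 x t½ ≥ 28, that is t½ ≥ 28/5 = 5.6 days. The first two results are then unchanged.

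**4. How many patients could be involved?** Table 5 lists five combination levels, and the 3+3 rule as written puts 3 to 7 patients in each.

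- If all five levels open without de-escalation: 5 x 3 = 15 to 5 x 7 = 35 combination patients.
- Under the planned Phase I total of about 45 (section 4.1): suppose all five monotherapy levels open and 800 and 1,200 µg are the two that must be confirmed in at least 6 patients each. Monotherapy then uses at least 3 + 3 + 3 + 6 + 6 = 21, leaving 45 - 21 = 24.

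The share of these patients who would be on ongoing ICI is not given, so the number affected lies between 0 and these ceilings.

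**The case against.** The strongest reply is that a specific, mandatory instruction should prevail over a general washout line. Section 3.1.1 says what shall happen to patients already on ICI, fixes their Cycle 1 Day 1, and requires a scan in the 30 days before IMSA101 is added. Following it is following the protocol, so section 11.7 is arguably not engaged, and a sensible site would ask the sponsor to confirm. On this view the gap is a slip of wording.

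Part of this stands. The intent is not in doubt, and asking the sponsor is a realistic fourth course. But the protocol states no order of precedence between 3.1.1 and 4.3, and a sponsor's confirmation leaves the written criterion unchanged.

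Other points also stand:

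- No effect on the RP2D has been demonstrated. The MTD depends on DLT counts, and replacement depends on early discontinuation for reasons other than DLT.
- The references to current ICI therapy in 8.1 and the synopsis are weak support, because they are used for combination patients generally, including de novo starters.
- The entry routes do not themselves require the ICI to be ongoing.

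The contradiction therefore rests on the add-on sentence in 3.1.1 and its copy in the synopsis. That is enough, because the sentence is explicit. The ceiling of 35 is loose, and 24 is closer to the planned size.

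**Conclusion.** The concern holds. Exclusion 1 is wrong as written: applied literally, it bars or forces washout of a group that the design explicitly enrols. It must be corrected, although the correction is small.

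The conflict reaches only Phase I combination patients still on an ICI at Cycle 1 Day 1, mainly those entering through the stable-disease or first-unconfirmed-progression routes. The per-patient figures in step 3 depend on the assumed dosing intervals and half-lives. The number of patients affected cannot be fixed from the documents. The finding concerns eligibility and conduct; it does not show that the dose decision would be biased.

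A separate, minor inconsistency becomes visible if such patients are enrolled as violations. Section 10.1.1 makes meeting the eligibility criteria a condition of the Safety Population, whereas the formal definition in 10.2.1 takes everyone dosed. Membership of a dosed but ineligible patient is therefore ambiguous. DLT, MTD and Cohort Review Committee decisions do not use that population.

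**What to change.** Add one clause to exclusion 1, identically in section 4.3 and the synopsis: *This does not apply to the PD-1/PD-L1 ICI that the patient continues as the combination partner in a Phase I combination cohort.*

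The same amendment can tidy three smaller points:

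- use one inequality for the half-life limb, since the synopsis has less than five and 4.3 has at most five;
- optionally, state that the four combination entry routes take precedence over inclusion 3 in those cohorts;
- delete the eligibility condition from the Safety Population sentence in 10.1.1 so that it agrees with 10.2.1.

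The cost is a text amendment: one clause in two places and a few words elsewhere. It needs no extra patients or procedures and leaves the escalation rules unchanged.
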